### Adverse events (Safety analysis)

Expected SAEs will be summarised as the number and proportion of patients experiencing at least one event. This will be done overall and by category. In addition, the total number of events will be reported.

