# 3.2.1. SF arm (Intervention group)

In this study, the SF condition means that participants will be provided with the Lexie Lumen hearing aids and will be asked to set up and manage the devices using the Lexie app, entirely without professional support, as would be standard for this OTC model. Hearing aids will be provided in their standard, consumer packaging, including all labelling and instructional material. Furthermore, they will be fitted according to the proprietary fitting algorithm (Lexie Comfort) using the in-situ thresholds obtained via the Lexie app. The fitting algorithm will be based on National Acoustics Laboratories' Non-Linear Version 2 (NAL-NL2) , with additional adjustments aimed for a greater listening comfort.

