# 3.2.2. Audiologist-fit arm (Control)

In the AF condition, participants will be provided with the same Lexie Lumen hearing aids fitted to match the National Acoustics Laboratories' Non-Linear Version 2 (NAL-NL2) acoustic gain prescriptions as closely as possible . AF fitting will be based on diagnostic audiometry conducted in a soundproof booth by the audiologist. Diagnostic audiometry will follow ISO 8253-1:2010 Acoustics — Audiometric test methods — Part 1: Pure-tone air and bone conduction audiometry guidelines. Participants in the AF group will be orientated on the use and management of the hearing aid by the audiologist.

**Figure 1.** Procedural description of the two groups of the randomized controlled trial. SF= self-fit; AF = audiologist fit.

The study will be conducted as two phases (four visits per participant). Phase I will be a two-week, take-home field trial after fitting the hearing aids. During the first 2-weeks no assistance or fine-tuning by the online Lexie hearing experts for the SF group will be allowed, and no fine-tuning by the audiologist in the AF group. This procedure will

be followed to isolate and only compare the benefit provided by the fitting without the help of online support or adjustment.

Phase II will commence at the first follow-up appointment on the third clinical visit. During this appointment, participants of the AF group will be allowed to request fine-tuning or assistance from the audiologist, if desired. The participants in the SF group will be informed that assistance could be sought through the Lexie online hearing experts, if desired. Phase II will be approximately 6 weeks in duration, and upon completion the final clinic visit and assessments will be conducted. Figure 2 provides an overview of the study protocol.

[figure not shown]

Figure 2. Trial timeline and design

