### 3.3. Sample size

This study aims to recruit 60 people (approximately 30 people in each group) with parallel allocation to the self-fit and audiologist fit groups. Sample size estimation is based on a previous OTC trial conducted by Sabin et al. 2020, who recruited similar sample sizes .

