# 4.2.2. Digits-in-Noise

Since the QuickSIN was developed in American English, one concern was that South African participants could have difficulty recognizing the words due to differences in dialect. Therefore, in addition to the QuickSIN, speech-in-noise performance will be measured using the South African English Digits-in-Noise test (DIN) (5,6). The DIN unaided and aided results will be measured following the same procedure as set for performing the QuickSIN).

Table 1. Timing of the assessments						
Visit	Baseline	Hearing Aid Fitting	2-week follow- up	6-week follow- up		
Pure tone audiometry	Х					
APHAB	X		Х	X		
IOI-HA			X	X		
QuickSIN	X		Х	Х		
DIN	X		X	X		
Real-Ear Measurement		Х		Х		

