# 5.3. Statistical analyses of primary and secondary endpoints

# Patient/ participant characteristics

Description of the baseline characteristics will be presented by treatment group. Discrete/ factor variables will be summarised by frequencies and percentages. Percentages will be calculated according to the number of participants for whom data are available. Continuous variables will be summarised by using mean and SD, and median and interquartile range (Q1-Q3).

Data that will be gathered include the following:

- Age
- Sex
- Pure tones average (based on audiogram performed by the audiologist)
- Ethnicity
- Level of previous hearing aid experience (Yes/No and duration)
- English proficiency (EF SET English proficiency score)
- Self-perceived degree of hearing loss (mild or moderate)

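### The safety analysis commits to a participant-level summary for expected SAEs only, and states no split by randomised arm

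*Combined protocol and SAP*

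**What the plan says.** The section Adverse events (Safety analysis), under 5.3, consists of three sentences.

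- The first sets the participant-level rule: "Expected SAEs will be summarised as the number and proportion of patients experiencing at least one event".
- The second gives the breakdown of that rule: "This will be done overall and by category".
- The third adds an event-level count: "In addition, the total number of events will be reported".

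The terms expected, SAE and category are not defined, and neither randomised arm is mentioned. Elsewhere in 5.3 the plan does name the groups. For baseline data it says "Description of the baseline characteristics will be presented by treatment group", and the APHAB, IOI-HA and speech-in-noise outcomes are all compared between groups.

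**The concern.** The section's title covers adverse events in general, but its only participant-level rule is limited to one class, serious events that are also expected. An analyst who follows the text exactly could leave out how many people had an unexpected serious event or a non-serious event, and would still comply with the plan.

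The arm matters because of what the trial compares. Under 3.2.2, control "participants will be provided with the same Lexie Lumen hearing aids", so the device itself is common to both arms. What differs is how it is fitted and supported. Self-fit participants set it up through the app from in-situ thresholds. Audiologist-fit participants are fitted from booth audiometry and orientated by the audiologist. A pooled summary describes the device, whereas any harm linked to the route of fitting can be seen only in a by-arm display. As written, neither is committed for unexpected or non-serious events at participant level.

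**Working it through.** The plan gives no safety figure to reproduce, so the check is mainly one of text.

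**Step 1. Apply the three sentences literally to each class of event.**

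| Class of event | Number and percentage of participants | Event count | By arm |
|---|---|---|---|
| Expected SAE | Committed, overall and by category | Committed | Not stated |
| Unexpected SAE | Not committed | Only if the third sentence is read widely | Not stated |
| Non-serious adverse event | Not committed | Only if the third sentence is read widely | Not stated |

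**Step 2. Consider the ambiguous third sentence.** On the narrow reading it counts expected SAEs only, and the other two classes do not appear at all. On the wide reading it counts every adverse event, and the other two classes enter a single total. That total cannot separate one participant with several events from several participants with one each. It also does not show seriousness or arm. The output therefore depends on the reading, but neither reading supplies the missing participant-level summary.

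**Step 3. Compare with the rest of 5.3.** Baseline characteristics, APHAB, IOI-HA and speech-in-noise each have a stated group presentation or comparison. The safety section has none. The undefined word category might have been meant to include arm, but the text does not say so.

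**Step 4. Check how the arms differ in support.** Section 3.2.1 describes self-fit set-up and management as "entirely without professional support, as would be standard for this OTC model". Sections 3.1 and 3.2.2 qualify this. The objective names remote support as part of the self-fit condition. The bar on help for the self-fit arm covers the first 2 weeks, during which the control arm also receives no fine-tuning. In Phase II, of about 6 weeks, self-fit participants may use the online hearing experts and control participants may ask the audiologist. The lasting differences are initial fitting, orientation and type of support.

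**Step 5. Context on resolution.** Section 3.3 states: "This study aims to recruit 60 people (approximately 30 people in each group". One affected participant is 1/30 = 3.3% of an arm and 1/60 = 1.7% overall. If no events are seen, the exact two-sided 95% upper limit is 1 − 0.025^(1/n):

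- n = 30: 1 − 0.025^(1/30) = 11.6%
- n = 60: 1 − 0.025^(1/60) = 6.0%

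These figures describe the precision of any safety table in this trial, before or after a change of wording. They do not measure the defect. They show only that a by-arm table would be descriptive and that the overall column is worth keeping beside it.

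**The case against.** The strongest reply is that this is a drafting matter. The section is titled for adverse events in general, its last sentence can be read to include all of them, and in a two-arm trial a group split may simply have been assumed. Safety is not among the endpoints in 4.3, and 30 per arm allows only coarse comparison. Most of this stands, and it is why the point is minor. It does not remove the gap, because even the most generous reading gives no participant-level figure for two classes of event and names no arm.

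Four stronger readings are tempting, and the documents do not support them.

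- **Deliberate exclusion.** A reader might infer that unexpected or non-serious events are being kept out of the report. The text omits them from one rule; it does not exclude them.
- **Events not collected.** A reader might note that none of the six rows of "Table 1. Timing of the assessments" concerns adverse events and infer that they would go unrecorded. That table schedules audiometry, questionnaires, speech tests and real-ear measurement. Its silence does not show how adverse events are collected.
- **Self-fit participants unsupported throughout.** The description in 3.2.1, taken alone, suggests this. Section 3.2.2 opens online help to them in Phase II, so the contrast between arms is narrower for most of follow-up.
- **A threat to the trial's conclusions.** Nothing in the safety section feeds the APHAB, IOI-HA, QuickSIN or DIN analyses.

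**Conclusion.** The concern holds as a minor gap in reporting. On its literal reading, the plan commits to participant-level safety figures for expected SAEs only, leaves the scope of the event total unclear, and states no presentation by arm. Its effect cannot be expressed as a number of events, because the documents give no event rate. What is affected is the completeness of the safety result; no primary or secondary conclusion changes. This rests on two assumptions: that the three sentences are applied as written, and that no safety analysis is specified in pages missing from the public text.

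**What to change.** Replace the three sentences of the section with:

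> All adverse events will be summarised by randomised arm and overall, as the number of events and the number and proportion of participants with at least one event, in separate rows for any adverse event, serious adverse events (expected and unexpected shown separately) and non-serious adverse events, and by type of event.

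The separate rows are needed. A sentence that only listed the classes included could be met by a single row for any adverse event, and the expected-SAE line that the plan now promises would be lost. Naming type of event takes the place of the undefined category.

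The change is one replaced section of the SAP, and the cost is a slightly longer safety table, which remains descriptive. It adds no visit, participant or hypothesis test, and Table 1 does not need to change.
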